6.3. Treatment Assignment

Subjects who meet the randomization criteria will be assigned to one of the 3 study treatments in accordance with the randomization schedule generated by Clinical Statistics, prior to the start of the study, using validated internal software.

Once a randomization number is assigned to a subject, it cannot be reassigned to any other subject in the study.

This study will utilize RAMOS NG, which will provide a means for central allocation of drug. Each investigator will be supplied with sufficient supplies to conduct the trial. Additional treatment packs will be supplied as needed to the sites. Details of how to use the RAMOS NG to randomize subjects is provided in the SRM.

The duration of treatment for each subject is 24 weeks. On the morning of each clinic study visit, subjects will refrain from taking their morning dose of study treatment until

instructed to do so by clinic personnel. On the other days during the treatment period (i.e. “non-clinic days”), subjects will be instructed to self-administer their study treatment in the morning and evening. Subjects should enter the time they take their study treatment in the eDiary.

Subjects will be randomly assigned to one of the blinded study treatment regimens in equal proportion (ratio of 1:1:1):

- UMEC/VI 62.5/25 mcg once daily via ELLIPTA + placebo twice daily via DISKUS
- UMEC 62.5 mcg once daily via ELLIPTA + placebo twice daily via DISKUS
- Salmeterol 50 mcg twice daily via DISKUS + placebo once daily via ELLIPTA

The randomisation will be stratified based on **long-acting bronchodilator** usage during the run-in (none, one or 2 **long-acting bronchodilators** per day).

Study treatment/investigational product will be dispensed at Visits 2, 3 and 4.

In order to ensure subjects have sufficient doses of study treatment, they must return to clinic within 30 days from V2, 60 and 90 days from V3 and V4 respectively (see Time and event table Section [7.1](#)).

Used study drug and rescue medication will be collected at Visits 3, 4 and 5 or at the Early Withdrawal Visit.

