6.7. Preparation/Handling/Storage/Accountability

No special preparation of the study treatment is required.

- The investigator or designee must confirm appropriate temperature conditions have been maintained during transit for all study treatment received and any discrepancies are reported and resolved before use of the study treatment.
- Only subjects enrolled in the study may receive study treatment and only authorized site staff may supply or administer study treatment. All study treatments must be stored in a secure environmentally controlled and monitored (manual or automated) area in accordance with the labelled storage conditions with access limited to the investigator and authorized site staff.
- The investigator, institution, or the head of the medical institution (where applicable) is responsible for study treatment accountability, reconciliation, and record maintenance (i.e. receipt, reconciliation and final disposition records).
- Further guidance and information for final disposition of unused study treatment are provided in the SRM.

All ELLIPTA DPI study treatment should be stored up to 25°C (77°F). Each All ELLIPTA DPI contains 30 doses and is packaged in a foil pouch with a desiccant sachet and stored in a carton. The inhaler should not be used for more than 30 days after opening the foil. The sites must maintain a daily temperature log for the investigational product.

Salmeterol DISKUS should be stored up to 25 °C.

Under normal conditions of handling and administration, study treatment is not expected to pose significant safety risks to site staff. Take adequate precautions to avoid direct eye or skin contact and the generation of aerosols or mists. In the case of unintentional occupational exposure notify the monitor, Medical Monitor and/or GSK study contact.

- A Material Safety Data Sheet (MSDS)/equivalent document describing occupational hazards and recommended handling precautions either will be

provided to the investigator, where this is required by local laws, or is available upon request from GSK.

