6.7.1. Study Treatment Return

All used and unused ELLIPTA and DISKUS inhalers and albuterol/salbutamol will be returned to GSK at the end of the study to be available for disposal. In some instances for sites outside the US, study supplies will be disposed of locally either by the site, the country medical department or third-party vendor. Detailed instructions for the return of the study drug can be found in the SRM.

Study treatment will be collected at Visit 3, 4 and 5 or at the Early Withdrawal Visit, if applicable.

For any ELLIPTA or DISKUS inhaler that fails to function properly, the subject should return to the clinic as soon as possible to obtain a new inhaler. The site will contact the RAMOS NG to obtain a new treatment pack number for the subject and dispense a new study treatment kit from the site's investigational product supply as instructed by the RAMOS NG

In addition, any ELLIPTA that fails to function properly must be identified and returned to GSK for testing.

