6.8. Compliance with Study Treatment Administration

When subjects self-administer study treatment(s) at home, compliance with study treatment(s) will be assessed through querying the subject during the site visits and through study drug compliance assessed at Visits 2, 3, 4 and 5 documented in the source documents and eCRF. A record of the number of ELLIPTA and DISKUS dispensed and the number of doses inhaled by each subject must be maintained and reconciled with study treatment and compliance records. Treatment start and stop dates, including dates for treatment delays if any will also be recorded in the eCRF.

Compliance with the ELLIPTA inhaler will be determined by reviewing the dose counter on the ELLIPTA. Compliance with the study DISKUS will be determined by reviewing the dose counter on the DISKUS. Subjects should be $\geq 80\%$ to $\leq 120\%$ compliant on taking study medication between each pair of on-treatment visits. Subjects who fall outside this range should be re-educated on treatment compliance by their site. This re-education should be documented in the subject's source document. If medication compliance repeatedly falls outside of acceptable ranges, the study sponsor/site monitor must be contacted to discuss subject eligibility for continued participation in the study.

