9.3. Data Analysis Considerations

9.3.1. Analysis Populations

Population	Definition / Criteria	Analyses Evaluated
All Subjects Enrolled (ASE)	
 All subjects for whom a record exists in the study database, including screen failures and any subject who was not screened but experienced an SAE between the date of informed consent and the planned date of the Screening visit. 	
 Subject Disposition Reasons for withdrawal prior to randomisation Inclusion, exclusion and randomisation criteria deviations SAEs for non-randomised

Population	Definition / Criteria	Analyses Evaluated
Intent-to-treat (ITT)	
 • All randomized subjects, excluding those who were randomized in error and received at least one dose of study medication. A subject who is recorded as a screen or run-in failure and also randomized will be considered to be randomized in error. Any other subject who receives a randomization number will be considered to have been randomized. • Displays will be based on the treatment to which the subject was randomized. 	
 • Study Population • Efficacy • Safety
Intent-to-treat ICS free (ITT ICS free)	
 • All subjects in the ITT Population who have not received ICS. 	
 • Study Population • Efficacy • Safety

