9.4.2. Other Analyses

The MMRM analysis will be repeated for the ITT ICS free population. Estimated differences between UMEC/VI or UMEC and Salmeterol will be presented together with 95% confidence intervals (CIs) for the difference and p-values.

Secondary and other efficacy endpoints and treatment comparisons will be adjusted for multiplicity as per Section [9.4.1](#).

Full details of the analyses to be performed on the other efficacy endpoints will be given in the RAP.

Safety Analyses

Adverse events (AEs) will be coded using the standard GSK dictionary, Medical

Dictionary for Regulatory Activities (MedDRA), and grouped by body system. The number and percentage of subjects experiencing at least one AE of any type, AEs within each body system and AEs within each preferred term will be presented for each treatment group. Separate summaries will be provided for all AEs, drug related AEs, fatal AEs, non-fatal SAEs, AESIs and AEs leading to withdrawal.

Deaths and SAEs will be documented in case narrative format.

Full details of the analyses to be performed on all safety endpoints will be given in the RAP.

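### Section 9.3.1 groups safety displays by randomised arm, so adverse events in a subject who took another arm's treatment are tabulated under a drug not taken (very small effect, cheap to correct)

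*Protocol*

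**What the plan says.** The table in section 9.3.1 defines three populations. All Subjects Enrolled covers safety only for serious events in subjects who were not randomised. ITT and ITT ICS free each list study population, efficacy and safety as their uses. The ITT row fixes the grouping: "Displays will be based on the treatment to which the subject was randomized". The ICS-free population is a subset of ITT and states no grouping rule of its own. No separate safety or as-treated population is defined.

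The safety part of section 9.4.2 plans "The number and percentage of subjects experiencing at least one AE of any type", with breakdowns by body system and preferred term, for each treatment group. It gives no rule for treatment received and leaves full detail to the reporting and analysis plan (RAP). It also states: "Deaths and SAEs will be documented in case narrative format".

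On supply, section 6.3 says: "This study will utilize RAMOS NG, which will provide a means for central allocation of drug". If an inhaler fails, section 6.7.1 says: "The site will contact the RAMOS NG to obtain a new treatment pack number for the subject", and the site dispenses the new kit from its own stock. The original protocol in the same file has the same population table and safety text as the amended one.

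**The concern.** Keeping subjects in their randomised arm protects the efficacy comparison. An adverse-event table answers a different question: what happened to people who took this drug. Section 7.4 names incidence of adverse events as the only safety endpoint, so the table by drug should reflect the drug taken.

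Under the stated rule, suppose a subject is randomised to salmeterol ("Salmeterol 50 mcg twice daily via DISKUS + placebo once daily via ELLIPTA") but is given the UMEC/VI arm's inhalers. Any event that follows is counted against salmeterol. The concern is confined to such subjects. What is at stake is the accuracy of a few cells, and it matters most for rare events, where one subject is a visible part of the count.

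This is not simply a detail left for later. Section 9.4.2 defers detail to the RAP, but section 9.3.1 has already stated the grouping. A RAP that follows the protocol carries the rule forward, and one that uses treatment received departs from it.

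**Working it through.** **Inputs.** Section 9.2 gives 727 evaluable subjects per arm, 10% withdrawal and approximately 808 randomised per arm. The protocol states no rate of wrong dispensing and no adverse-event rate, so the effect is worked out per misallocated subject.

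**The plan's figure.** 727 / (1 − 0.10) = 807.8, rounded up to 808 per arm. 3 × 808 = 2424, which matches section 4.3.

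**One subject, general bound.** Let n = 808. A subject who had the event is moved from the randomised arm (x events) to the arm whose treatment was taken (y events).

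- Arm left: x/n − (x − 1)/(n − 1) = (n − x)/(n(n − 1)). This is largest at x = 1, where it equals 1/808 = 0.124 points.
- Arm joined: (y + 1)/(n + 1) − y/n = (n − y)/(n(n + 1)). This is largest at y = 0, where it equals 1/809 = 0.124 points.
- Between-arm difference: the shift is at most 1/808 + 1/809 = 0.247 points.

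**Rare event, illustrative counts.** 3/808 v 0/808 is 0.371% v 0%, a difference of 0.371 points. After the move, 2/807 v 1/809 is 0.248% v 0.124%, a difference of 0.124 points.

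**Common event, illustrative counts.** 323/808 in each arm is 39.975% v 39.975%. After the move, 322/807 v 324/809 is 39.901% v 40.049%, a shift of 0.149 points.

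**Several subjects, assumed number k.** If all k subjects had the event and all moved the same way, the shift is at most k/808 + k/(808 + k).

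| k (assumed) | Largest shift, points |
|---|---|
| 0 | 0 |
| 1 | 0.247 |
| 2 | 0.494 |
| 3 | 0.741 |
| 4 | 0.988 |

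The range for k is an assumption, and each entry is a worst case.

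**The case against.** The strongest case for leaving the text alone is that the rule is prespecified, contradicts nothing, keeps the randomised comparison and keeps safety and efficacy denominators aligned. Drug is allocated centrally, section 9.1 states no safety hypothesis, and deaths and serious events receive narratives. All of this stands. It limits the size of the point, but it does not make the randomised arm the right label for a drug that was not taken.

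A second objection is that regrouping would move very few subjects. That is also true. Treatment lasts 24 weeks (168 days) and each ELLIPTA holds 30 doses, so a completer uses about six. One wrong replacement inhaler leaves most of the exposure on the randomised treatment. For such subjects the useful addition is the listing.

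Three stronger readings are tempting, but the documents do not support them:

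- A reader might infer that safety differences will be materially diluted. If a share e of each of two arms took the other's treatment throughout, the difference would shrink by the factor 1 − 2e. With assumed risks of 10% v 5%, e = 1% (about 8 of 808 per arm) turns 5.00 points into 4.90. The protocol gives no value for e, and the model needs a complete exchange of treatments.
- A reader might try to count which inhaler mix-ups produce another arm's treatment and which match no arm. That depends on whether the two inhalers are dispensed separately. Section 6.7.1 speaks of a treatment kit without saying whether it holds one inhaler or both.
- A reader might take site records as a stated source of pack identity. Section 6.8 says "A record of the number of ELLIPTA and DISKUS dispensed and the number of doses inhaled by each subject must be maintained", and section 6.7 requires receipt, reconciliation and disposition records. These are a likely source, but neither section says that they show which pack each subject received.

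**Conclusion.** The point holds as a minor one. Section 9.3.1 states a rule that credits adverse events to a drug not taken whenever a subject took another arm's treatment, and section 9.4.2 does not correct it. For each such subject with the event, the shift in a between-arm difference is at most about 0.25 points with 808 per arm. It is zero if no wrong treatment is dispensed.

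The bound rests on the planned arm size and on counting each subject once. How many subjects would be affected cannot be derived from the protocol. No efficacy result, sample size, significance level or safety conclusion is put at risk. The RAP was not available and may already handle the matter, but it would have to depart from the protocol to do so. This is an optional improvement.

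**What to change.** In section 9.3.1, limit the sentence on displays to study-population and efficacy displays, and add:

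> *Safety displays will be based on the treatment actually received; a subject who received more than one study treatment is counted once, under the treatment taken for the greater part of the treatment period, and every subject given a wrong pack is listed with adverse events, onset dates and the treatment being taken at onset.*

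Two details are worth settling at the same time, before unblinding:

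- **Ties.** The supply from Visit 4 covers Weeks 12 to 24, nominally half of the period. An equal split therefore needs a default, and the randomised treatment is the natural one.
- **No matching arm.** A subject left on a pair of inhalers that is no study arm has no arm to move to. That subject can stay under the randomised treatment and appear in the listing.

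Site accountability records are the likely source for the pack actually given. RAMOS NG alone shows the pack that should have been given. The sponsor should confirm that the site records hold pack identity.

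The cost is a few sentences, one listing, and reconciliation of site records against RAMOS NG for suspected wrong packs. The downside is that safety and efficacy denominators by arm may differ by a few subjects, which a table footnote can explain.

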9.3.2. Interim Analysis

No interim analysis is planned for the study.

9.4. Key Elements of Analysis Plan

Treatment Comparisons

The primary treatment comparison of UMEC/VI with UMEC will be performed on the ITT population.

The other treatment comparisons of UMEC/VI and UMEC with Salmeterol will be performed on the ITT population and ITT ICS free population.

9.4.1. Primary Analyses

The treatment comparison of primary interest will be UMEC/VI versus UMEC for the primary endpoint of change from baseline in trough FEV₁ at Week 24. The primary analyses will be performed using a mixed model repeated measures (MMRM) analysis and will be based on a two-sided hypothesis testing approach on the ITT Population.

In order to account for multiplicity across treatment comparisons and endpoints, a step-down closed testing procedure will be applied whereby inference for secondary and other endpoints or treatment comparisons are dependent upon statistical significance having been achieved for the primary comparison. If the primary comparison is significant i.e. the associated p-value for UMEC/VI versus UMEC for change from baseline in trough FEV1 at Week 24 is below 0.05, this will allow inference of treatment comparisons (UMEC/VI versus UMEC on all other endpoints, and UMEC/VI versus Salmeterol and UMEC versus Salmeterol on all endpoints including the primary endpoint), which will be declared statistically significant if the associated p-value is below 0.05.

There will be 2 analyses one for one for the German Federal Joint Committee (G-BA) and one for the rest of the world (ROW).

The step-down closed testing procedure only applies to the ROW. For the G-BA statistical inference for secondary and other endpoints or treatment comparisons will not be conditional on achieving statistical significance of the primary comparison.

The primary endpoint of mean change from baseline in trough FEV1 at the end of Week 24 and secondary endpoint change from baseline in TDI score at Week 24 will both be analysed using MMRM analysis. The MMRM analysis for change from baseline in trough FEV1 and TDI will include measurements at Treatment Weeks 4, 12 and 24. Treatment group (a categorical variable) will be fitted as the explanatory variable with appropriate pre-defined variables, stratum (number of bronchodilators per day during run-in) and baseline values, fitted as covariates. Visit (nominal) will be fitted as a categorical variable and visit-by-baseline and visit-by-treatment interaction terms will be included to allow treatment effects to be estimated at each visit separately. The variance covariance matrix will be assumed to be unstructured (based on previous experience no issues are expected with fitting models with this matrix structure).

While missing data are not explicitly imputed in the primary MMRM analyses, there is an underlying assumption that the data are missing at random.

The estimated treatment differences between UMEC/VI versus UMEC for each endpoint will be presented with the 95% confidence intervals for the difference and the p-value.

Full details of the analyses to be performed on all primary endpoints will be given in the RAP.

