1. PROTOCOL SYNOPSIS FOR STUDY 201749

Rationale

The primary purpose of this study is to demonstrate improvements in lung function in subjects treated with Umeclidinium/Vilanterol (UMEC/VI) compared with Umeclidinium (UMEC) for 24 weeks. A further important aspect of the study is to evaluate the effect of UMC/VI, UMEC, and salmeterol with respect to health-related quality of life (HRQoL), measured through patient reported outcomes (PROs) questionnaires, and lung function. Additional assessments to further evaluate other measures of chronic obstructive pulmonary disease (COPD) efficacy and symptoms control will be performed.

Objective(s)/Endpoint(s)

Objectives	Endpoints
Primary	
 To compare the effect of UMEC/VI (62.5/25 mcg once daily) with UMEC (62.5 mcg once daily) on lung function Change from baseline in trough Forced Expiratory Volume in One Second (FEV₁) at week 24
Secondary	
 To compare UMEC/VI (62.5/25 mcg once daily), UMEC (62.5 mcg once daily) with salmeterol (50 mcg twice daily) on patient reported outcomes (PROs) Change from baseline in self administered computerised (SAC) transient dyspnea index (TDI) Percentage of TDI responders according to SAC TDI score. A responder is defined as a ≥ 1 unit improvement in SAC TDI score Assessment of respiratory daily symptoms over 24 weeks using Evaluating Respiratory Symptoms-COPD (E-RS) and its subscales (breathlessness, cough and sputum and chest symptoms) Percentage of E-RS responders according to E-RS score (defined as reduction in E-RS score of ≥ 2 or ≥ 3.35 units) from baseline Change from baseline in St George's Respiratory Questionnaire (SGRQ-C) Percentage of responders according to SGRQ-C total score (defined as a 4 point or greater reduction from

Objectives	Endpoints
	
baseline)
 
 • Change from baseline in COPD assessment test (CAT) • Percentage of responders according to CAT (defined as a ≥ 2 unit improvement in score from baseline)

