9.2. Sample Size Considerations

The primary endpoint is change from baseline in trough FEV₁ at Week 24. As an important aim of the study is to compare UMEC/VI, UMEC and salmeterol with respect to HRQoL the sample size has been calculated to provide sufficient power for the comparison of the primary and secondary endpoint TDI, at Week 24.

The sample size calculations use a two-sided 5% significance level and an estimate of between subject standard deviation for TDI of 2.94 units. The estimate of SD is based on DB2113373 [[Donohue](#), 2013], a study which consisted of treatment arms of UMEC/VI 62.5/25, UMEC 62.5 VI (Vilanterol) 25mcg and placebo and is the value at Day 168 in a subgroup of subjects who were ICS free at screening. Based on these data, 727 evaluable subjects per treatment arm will be required to provide 90% power to detect a statistically significant difference if the true difference is 0.5 units, $\frac{1}{2}$ the MCID, between UMEC/VI and UMEC. The smallest observed effect predicted to result in a statistically significant difference between treatment groups is 0.31 units.

With this number of evaluable subjects per arm, the study will have >99% power assuming a true treatment difference of 80mL between UMEC/VI and UMEC for trough FEV₁ at 24 weeks at the two-sided 5% significance level. This calculation uses a SD for trough FEV₁ of 240mL, based on prior results for trials comparing dual bronchodilators versus single bronchodilators ([Donohue](#), 2013; [Bateman](#), 2013). The smallest observed effect predicted to result in a statistically significant difference between treatment groups is 25mL.

In order to account for a 10% withdrawal rate, approximately 808 subjects per treatment arm will be randomised.

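### The ROW multiplicity procedure in 9.4.1 is a single gate on the primary comparison and gives no strong familywise control beyond it, although 9.4.1 and 9.4.2 say multiplicity is accounted for

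*Protocol*

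**What the plan says.** Section 9.4.1 gives the purpose and the method in one sentence: "In order to account for multiplicity across treatment comparisons and endpoints, a step-down closed testing procedure will be applied". The content of the procedure is that "inference for secondary and other endpoints or treatment comparisons are dependent upon statistical significance having been achieved for the primary comparison". Once the primary comparison has p<0.05, the hypotheses released are "UMEC/VI versus UMEC on all other endpoints, and UMEC/VI versus Salmeterol and UMEC versus Salmeterol on all endpoints including the primary endpoint". The section then sets one criterion for every hypothesis in that set: "which will be declared statistically significant if the associated p-value is below 0.05".

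The same section sets out two analyses, one for the German Federal Joint Committee (G-BA) and one for ROW. It limits the procedure: "The step-down closed testing procedure only applies to the ROW". For G-BA, inference on the remaining endpoints does not depend on the primary result.

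Section 9.4.2 refers back: "Secondary and other efficacy endpoints and treatment comparisons will be adjusted for multiplicity as per Section" 9.4.1.

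Section 9.2 says of the primary comparison that "the study will have >99% power assuming a true treatment difference of 80mL between UMEC/VI and UMEC for trough FEV₁ at 24 weeks". It sizes the trial on the secondary endpoint TDI.

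**The concern.** A closed test rejects a hypothesis only if every intersection containing it is also rejected at level alpha. A step-down procedure has successive steps, each conditional on the one before. The rule in 9.4.1 has one step and then an unordered set of tests, each at the full 0.05. It therefore does not deliver what 9.4.1 says it is for, namely control across both endpoints and treatment comparisons, and the statement in 9.4.2 points to an adjustment that is not there.

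What is at stake is the patient-reported outcomes. Section 9.2 treats them as an important aim and takes the sample size from TDI. Under the present wording, any secondary or other result with p<0.05 in the ROW report could be described as multiplicity-adjusted when it has only passed a nominal test. Two features enlarge the set further. The E-RS responder endpoint has two cut-offs ("defined as reduction in E-RS score of ≥ 2 or ≥ 3.35 units"), and 9.4 runs the salmeterol comparisons in both the ITT and the ITT ICS free populations.

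**Working it through.** **Inputs (Protocol 9.2).** Two-sided 5% level; 727 evaluable subjects per arm; trough FEV1 difference 80 mL, SD 240 mL; TDI difference 0.5 units, SD 2.94. Allocation is 1:1:1 (6.3).

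**1. The plan's own figures reproduce.**
- TDI sample size: n = 2(1.960 + 1.282)² × 2.94² / 0.5² = 726.6, so 727 per arm, as stated.
- Primary power: SE = 240 × √(2/727) = 12.59 mL; 80/12.59 = 6.36 SE; power 0.99999, consistent with the stated >99%.

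The sample-size arithmetic is not at fault.

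**2. How often the gate opens.** If the 80 mL effect is real, with probability above 0.9999. If the true effect were half that, 40 mL, then 40/12.59 = 3.18 SE and the gate still opens about 89% of the time. If the primary null is true, it opens about 5% of the time (simulated 0.048 to 0.051).

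**3. One null endpoint, three comparisons.** Take a single endpoint with no difference between any arms, such as TDI alone. The three pairwise tests share arms, so the chance that at least one has |z| > 1.96 is the chance that the range of three standard normal values exceeds 1.96√2. This is 0.12. No assumption about correlation between endpoints is needed.

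**4. The eight listed secondary endpoints.** Section 3 lists eight, so 8 × 3 = 24 tests. I simulated null arm means for three arms, with the pairwise tests sharing arms and a common correlation between endpoints. The protocol gives no correlation, so it is an assumption and is shown as a range.

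| Assumed correlation | 0 | 0.3 | 0.5 | 0.7 | 0.9 |
|---|---|---|---|---|---|
| P(at least one false claim), 24 null tests | 65% | 59% | 51% | 40% | 27% |

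The expected number of false claims is 24 × 0.05 = 1.2 at any correlation.

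**5. The full released set.** Section 3 lists 12 other endpoints. One of them is trough FEV1 again, leaving 11 new ones. The gate therefore releases (8 + 11) × 3 = 57 tests plus the two salmeterol comparisons on the primary endpoint, 59 in all, before counting E-RS subscales, the second cut-off or the second population. For the 57, if all are null, the chance of at least one false claim is about 92%, 84%, 72% and 45% at correlation 0, 0.3, 0.5 and 0.8.

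**The case against.** Four points can fairly be made for the plan.

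- **The gate does something.** It keeps the primary test at 0.05 and, if the primary null is true, holds the chance of any ROW false claim near 0.05. A reader might infer that there is no multiplicity control at all; the documents do not support that. What is missing is strong control past the primary. The probability above 0.9999 also presumes that the 80 mL effect is real.
- **The all-null case is the worst case.** Section 9.2 itself plans for a true TDI difference of 0.5. Where secondary effects are real, fewer nulls remain and the risk falls. A reader might conclude that a chance finding among the secondaries is very likely, or quote 1 − 0.95²⁴ = 71%. That figure treats the three comparisons as independent although they share arms; with uncorrelated endpoints the figure is 65%. The correlation is probably appreciable, since each of the four instruments is listed as both a score and a responder rate. With 0.8 within such pairs and 0.5 between them, the figure is about 47%.
- **G-BA is openly exempt.** No error control is claimed there, so the inconsistency concerns ROW.
- **Analysis detail is deferred to the RAP.** This does not help. The threshold, the released set and the name of the procedure are fixed in 9.4.1. A RAP that follows them inherits the problem, and one that departs from them contradicts the protocol.

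It is also true that this is a Phase IV study of marketed doses and that the primary hypothesis, its alpha, the sample size and the data collected are unaffected. That limits the consequence but does not make the statement accurate.

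**Conclusion.** Wrong as written, for the ROW analysis. The primary test is sound. Beyond it, the stated rule provides weak control only, under the primary null, while 9.4.1 and 9.4.2 describe control across endpoints and comparisons.

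The most robust figure is 0.12 for one null endpoint over three comparisons. For the eight secondary endpoints it is about 27% to 65%. The second range rests on all 24 nulls being true, on a common between-endpoint correlation from 0.9 down to 0, and on the gate being open, which is near certain on the plan's assumptions.

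Nothing here shows that any particular secondary result will be false, or that the trial is the wrong size. Nor do the documents dictate a test order beyond the case for TDI, which follows from its role in the sample size.

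**What to change.** **Minimum.** In 9.4.1 and 9.4.2, remove the description of the procedure as step-down closed testing and the statement that secondary and other endpoints are adjusted for multiplicity. Keep the gate if wanted, and state that ROW p-values past the primary comparison are nominal. This alone makes the text accurate.

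**Better, for ROW.** Add a short fixed sequence at two-sided 0.05 on the ITT population, stopping at the first non-significant test:
1. Week 24 trough FEV1, UMEC/VI versus UMEC.
2. Week 24 SAC TDI, UMEC/VI versus UMEC.
3. A short named list chosen by the sponsor that addresses the salmeterol comparisons, including UMEC versus salmeterol if a claim is wanted, since it falls under a stated secondary objective.

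Everything else, including one of the two E-RS cut-offs and the ICS-free repeats, is nominal.

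**G-BA.** State that this analysis is not multiplicity-controlled.

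**Cost.** Wording only, with no change to sample size or data collection. TDI in second place keeps its power: 0.99999 × 0.900 is at least 0.90 to two decimals if the two tests are taken as independent. The price is that fewer endpoints can carry a confirmatory claim.
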